5.4.2.4 Secondary Endpoint (Pharmacokinetics)

- **Plasma concentration of AT-511, AT-551, AT-229, and AT-273 at specified timepoints**

The PK analysis population will consist of patients with sufficient data to enable estimation of key parameters (including, but not limited to, maximum concentration [C_{max}] and minimum concentration), with patients grouped according to treatment received.

Due to sparse sampling, non-compartmental analysis will not be performed.

Samples taken for PK analysis will be processed to plasma and concentrations of AT-511 (free base form of AT-527) and its major metabolites AT-551, AT-229, and AT-273, will be quantified by a validated liquid chromatography-tandem mass spectrometry method.

For AT-511, AT-551, AT-229, and AT-273 plasma concentration-time profiles will be plotted

- By cohort,

- Overlaying arithmetic mean and individual values (log concentration scale)
- Overlaying arithmetic mean (+ SD) and individual values (linear concentration scale)
- Overlaying individual plots (linear and log concentration scale)
- Group by cohort
 - Overlaying arithmetic mean (log concentration scale)
 - Overlaying arithmetic mean (+ SD) (linear concentration scale)

Individual PK concentration data will be listed by cohort.

Descriptive summary statistics tables for PK concentration data will be provided by cohort and visit/sampling timepoint. Summary statistics will include mean (arithmetic and geometric), SD, CV (arithmetic and geometric), median, minimum, and maximum. Concentrations below the lower limit of quantification (LLOQ) will be treated as zero in summary statistics and for PK parameter calculations.

Nonlinear mixed effects (NLME) modeling may be used to analyze the dose-concentration-time data of AT-511 and AT-273 in plasma. Population and individual PK parameters (e.g., CL/F and V_{ss}/F) will be estimated and the influence of various covariates (such as age, gender and body weight) on these parameters will be investigated. The data collected during this study may be pooled with data collected in other clinical studies (previous Phase I and/or Phase II study in healthy volunteers and HCV-infected patients) as appropriate to build the pharmacokinetic model. Secondary PK parameters such as AUC and C_{max} may be derived from the individual post-hoc predictions. Results of the NLME PK analysis will be reported in a standalone document separate from the Clinical Study Report (CSR).

Additional PK analyses may be conducted as appropriate. The PK data and parameters derived from these analyses may be used for exploratory graphical analyses of the pharmacodynamic (PD) data and parameters.

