6.6 PHARMACOKINETIC ANALYSES

The PK analysis population will consist of patients with sufficient data to enable estimation of key parameters (including, but not limited to C_{max}, and minimum concentration), with patients grouped according to treatment received. Due to sparse sampling, non-compartmental analysis will not be performed.

Samples taken for pharmacokinetic analysis will be processed to plasma and concentrations of AT-511 (free base form of AT-527) and its major metabolites AT-551, AT-229, and AT-273, will be quantified by a validated liquid chromatography-tandem mass spectrometry method.

Descriptive summary statistics for PK concentration data will be provided by cohort and visit/sampling time point. Concentrations below the lower limit of quantification (LLOQ) will be reported as zero. Summary statistics will include mean (arithmetic and geometric), SD, CV (arithmetic and geometric), median, minimum, and maximum. Concentrations below LLOQ will be treated as zero in summary statistics and for PK parameter calculations.

Nonlinear mixed effects (NLME) modeling may be used to analyze the dose-concentration-time data of AT-511 and AT-273 in plasma. Population and individual PK parameters (e.g., CL/F and V_{ss}/F) will be estimated and the influence of various covariates (such as age, gender and body weight) on these parameters will be investigated. The data collected during this study may be pooled with data collected in other clinical studies (previous Phase I and/or Phase II study in healthy volunteers and HCV-infected patients) as appropriate to build the pharmacokinetic model. Secondary PK parameters such as AUC and C_{max} may be derived from the individual post-hoc predictions. Results of the NLME PK analysis will be reported in a standalone document separate from the Clinical Study Report.

The exposure-response profile of AT-511 and its major metabolites will be explored (e.g., relationship between plasma concentration of AT-273 and antiviral activity) and will be reported in a standalone document separate from the Clinical Study Report.

Additional PK analyses may be conducted as appropriate. The PK data and parameters derived from these analyses may be used for exploratory graphical analyses of the PD data and parameters.

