- ^w After informed consent has been obtained but prior to initiation of study drug, only serious adverse events caused by a protocol-mandated intervention should be reported. After initiation of study drug, all adverse events will be reported until the end of study follow-up telephone call on Day 33.

Appendix 4

Schedule of Pharmacokinetic Samples

	Cohort A	Cohorts B–E		
	BID Regimen	BID Regimen	TID Regimen	QD Regimen
Day 1	Predose ^{a, c}	Predose ^{a, c}	Predose ^{a, c}	Predose ^{a, c}
	1 and 3 hours postdose ^{b, c}	1 and 4 hours postdose ^{b, c}	1 hour postdose ^{b, c} Predose [with reference to second dose of the day] ^{a, c}	1 and 4 hours postdose ^{b, c}
Day 3	Predose ^{a, c}	Predose ^{a, c}	Predose ^{a, c}	Predose ^{a, c}
Day 5	Predose ^{a, c} and 3 hours postdose ^{b, c}	Predose ^{a, c}	Predose ^{a, c}	Predose ^{a, c}
		1 and 4 hours postdose ^{b, c} Predose [with reference to second dose of the day] ^{a, c}	1 hour postdose ^{b, c}	1 and 4 hours postdose ^{b, c}
Day 7	48 (\pm 1) hours ^{c, e}	Anytime ^{c, d}	Anytime ^{c, d}	Anytime ^{c, d}
Early termination	—	Sample to be collected if early termination occurs on or before Day 7		

BID = twice a day; QD = once a day; TID = three times a day.

Note: Unless otherwise specified (TID regimen), all timepoints are in relation to the first dose administered on a given day.

^a Predose sampling window: within 30 minutes prior to dose administration.

^b Postdose sampling window: \pm 30 minutes from scheduled sampling time.

^c For patients at participating sites who have provided written or electronic informed consent to participate in mobile nursing visits, this assessment or procedure may be performed by a trained nursing professional at the patient's home.

^d The exact sampling time will be captured in relation to the time of last (10th) dose.

^e In Cohort A, the 48-hour PK sampling on Day 7 is with reference to the first dose on Day 5.

Appendix 5
COVID-19 Symptom Diary
and Patient Global Impression of Severity

Do not reproduce or distribute. The Sponsor will provide sites with all instruments to be completed in this study.

Note that the following is a sample. Sites will be provided with separate versions of the diary for Days 1–14 (morning vs. evening, including recording of temperature) and Days 15–28 (evening, including recording of temperature).

Today's date: _____ Time completing: _____

COVID-19 Evening Symptom Diary

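### Setting PK concentrations below LLOQ to zero makes the planned geometric mean zero and the geometric CV undefined wherever a sampling timepoint contains such a value

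*SAP*

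**What the plan says.** SAP 5.4.2.4 sets the unit of summary: "Descriptive summary statistics tables for PK concentration data will be provided by cohort and visit/sampling timepoint". It then names the statistics: "Summary statistics will include mean (arithmetic and geometric), SD, CV (arithmetic and geometric), median, minimum, and maximum". The sentence after that gives the handling rule: "Concentrations below the lower limit of quantification (LLOQ) will be treated as zero in summary statistics and for PK parameter calculations".

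Protocol 6.6 lists the same statistics and agrees on the rule: "Concentrations below LLOQ will be treated as zero in summary statistics and for PK parameter calculations". It also says: "Concentrations below the lower limit of quantification (LLOQ) will be reported as zero".

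The SAP plans concentration-time plots by cohort as well, including one described as "Overlaying arithmetic mean and individual values (log concentration scale").

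Neither document exempts the geometric statistics from the zero rule, substitutes a positive value, excludes the zeros, or says that a cell will be left blank when BLQ values are present. The number of BLQ values is not among the listed statistics.

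**The concern.** The two instructions cannot both be carried out in a cell that holds a BLQ value. A geometric mean is built from logarithms, and the logarithm of zero does not exist. A programmer following the text must either report a zero or an error, or improvise a rule that is written down nowhere. The obvious improvisations are dropping the zeros or replacing them with a positive value, and they give different answers. Since the tables need not show how many values were BLQ, a reader could not tell which was done.

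Plasma concentration of AT-511 and its three metabolites is a stated secondary endpoint. What is at stake is whether its geometric summaries can be computed and reproduced at the low-concentration timepoints.

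**Working it through.** The plan attaches no numerical result to this point, so there is no figure to reproduce. The check is of the definitions.

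**Inputs from the documents**
- BLQ = 0 in summary statistics; geometric mean and CV required by cohort and timepoint (SAP 5.4.2.4, Protocol 6.6).
- Sampling (Protocol Appendix 4): predose on Days 1, 3 and 5 in every cohort. The window is "Predose sampling window: within 30 minutes prior to dose administration". There is also a Day 7 sample. For one cohort its timing is stated: "In Cohort A, the 48-hour PK sampling on Day 7 is with reference to the first dose on Day 5". For Cohorts B–E on Day 7 it may be taken at any time.
- Active patients (Protocol 6.1): Cohort A 60 × 1/2 = 30; Cohorts B–D 40 × 3/4 = 30 each; Cohort E 112.

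**Definitions**
- Geometric mean = exp(mean of ln x) = (product of the x)^(1/n).
- Geometric CV = 100 × √(exp(variance of ln x) − 1).

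**Step 1: one zero in a cell.** The product contains a factor 0, so the geometric mean is exactly 0. In the log form ln 0 is minus infinity, and some software returns missing. The variance of ln x does not exist, so the geometric CV is undefined. The result is the same for any number of zeros. The arithmetic mean stays defined.

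**Step 2: which cells.** The Day 1 predose sample precedes any study drug, so every value there is expected to be BLQ. The geometric mean is 0 and the geometric CV undefined; the arithmetic CV is also undefined (0/0). At the Day 3 and Day 5 predose and Day 7 samples, a BLQ value is possible. Neither an LLOQ nor a BLQ rate is given.

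**Step 3: how easily a later cell is hit.** P(at least one BLQ) = 1 − (1 − p)^n, with p assumed and patients independent:

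| Assumed BLQ rate p | n = 30 | n = 112 |
|---|---|---|
| 1% | 26% | 68% |
| 2% | 45% | 90% |
| 5% | 79% | 99.7% |
| 10% | 96% | >99.9% |

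For example, 1 − 0.99^30 = 0.260.

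**Step 4: why an improvised rule is not harmless.** This uses 30 simulated lognormal values (median 100, log-SD 0.5, arbitrary units), whose geometric mean is 96.7 and geometric CV 44% when all are quantifiable. The lowest values are then declared BLQ:

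| Number BLQ | Zero rule | BLQ excluded | LLOQ/2 = 5 (assumed) |
|---|---|---|---|
| 1 | 0; undefined | 101.3; 36% | 91.6; 72% |
| 3 | 0; undefined | 107.5; 27% | 79.1; 125% |
| 6 | 0; undefined | 113.3; 24% | 60.7; 206% |

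The substituted value matters too. With 3 BLQ, the geometric mean is 107.5^(27/30) × v^(3/30). For v = 1 this is 67.4 and for v = 20 it is 90.9, with geometric CVs of 268% and 62%. These figures show that the choice moves the answer. They do not predict this trial's results.

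**Step 5: comparison inside the SAP.** For viral RNA, SAP 5.3.2 replaces results that are positive but below the limit with 119 copies/mL and negative results with 60 copies/mL before taking log10. The PK section has no equivalent step.

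**The case against.** The strongest reply is that this is a small gap in descriptive tables. Much of that stands. The only cells affected by design are Day 1 predose, where a geometric mean carries no information. Cells without BLQ values are untouched. Median, minimum, maximum, arithmetic mean and SD remain defined, the planned mean plots use arithmetic means, and individual concentrations are to be listed, so no data are lost. No test, confidence interval or power figure depends on the geometric statistics. A printed 0 or not-calculable entry would also be conspicuous.

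Three stronger readings are tempting, and the documents do not support them.

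- Because the zero rule also covers PK parameter calculations, a reader might infer that zeros would enter the nonlinear mixed-effects model and distort its residual error. Both documents make that model optional and place its report outside the Clinical Study Report. Neither says how BLQ values would enter it.
- A reader might infer that predose troughs are likely to be BLQ. No LLOQ, BLQ rate or plasma half-life is given for any of the four analytes, so only possible can be said.
- A reader might infer that dose decisions are compromised. The regimens for Cohorts B–D are described as following safety reviews. Cohort E takes a regimen from an earlier cohort, and no text ties that choice to these tables. Exposure-response work is reported separately, and nothing says it draws on them.

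What the reply does not remove is that the rule, followed literally, gives an unusable result in any affected cell, and the text offers no authorised way round it.

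**Conclusion.** The point holds, limited to geometric means, geometric CVs and log-scale plots in analyte-by-timepoint cells with at least one BLQ value. There the written rule gives a geometric mean of 0 (or missing) and an undefined geometric CV, and zeros cannot be drawn on a log axis. That conclusion follows from the definitions and needs no assumption about the trial.

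How often it would occur after Day 1 is unknown. The range of 26% to 96% for a cell of 30 active patients rests on assumed BLQ rates of 1% to 10%, independence between patients, and a sample from every patient. The primary virology analysis is not affected. This is a rule that is wrong as written for a secondary descriptive endpoint; it should be corrected, but it does not threaten the trial's main conclusions.

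**What to change.** Replace the BLQ sentence in SAP 5.4.2.4, and align Protocol 6.6, with a short paragraph that does four things:

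1. Limits the zero rule to arithmetic summaries.
2. Adds the number and percentage BLQ at each timepoint to the listed statistics.
3. Prespecifies, for geometric statistics and log-scale plots, a rule that does not use zero. LLOQ/2 for post-dose BLQ values is one option. Excluding BLQ values, with the count shown, is another. Since the two differ, one must be named in advance.
4. Shows geometric statistics as not calculated at Day 1 predose and wherever the BLQ fraction exceeds a stated limit.

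The cost is one paragraph in each document and a small change to table specifications. No new data, visits or patients are needed.

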5.4.2.5 Sensitivity Analyses for Secondary Endpoints

Due to practical constraints, patients may receive first study treatment a day post randomization. Sensitivity analyses may be performed on the following time-to-event virology and efficacy secondary endpoints, defined as the time from randomization to meeting the endpoint:

- Time to cessation of SARS-CoV-2 viral shedding as measured by RT-PCR
- Time to sustained non-detectable SARS-CoV-2 virus RNA
- Time to alleviation or improvement of COVID-19 symptoms (Items 1–12 of the COVID-19 symptom diary)
- Time to alleviation of COVID-19 signs and symptoms

Sensitivity analyses may also be performed for the following time-to-event virology secondary endpoints where results reported as BLQ are treated as positive (instead of negative):

- Time to cessation of SARS-CoV-2 viral shedding as measured by RT-PCR
- Time to sustained non-detectable SARS-CoV-2 virus RNA

5.5 EXPLORATORY ENDPOINTS ANALYSIS

Exploratory Virology Endpoint Analyses

The following virology exploratory endpoints will be compared between each AT-527 dose group and the pooled placebo group:

- Treatment-emergent amino acid substitutions in SARS-CoV-2 viral genes (nsp12 and potentially other genes)
- Anti-SARS-CoV-2 antibody status/titer at specified timepoints
- Change from baseline in SARS-CoV-2 virus titer at specified timepoints
- Time to cessation of SARS-CoV-2 viral shedding as measured by virus titer
- Proportion of patients with positive SARS-CoV-2 virus titer at specified timepoints
- AUC of SARS-CoV-2 virus titer
- Drug susceptibility in patients with evaluable virus at specified timepoints

Polymorphic and treatment-emergent substitutions in nsp12 and potentially other genes will be reported descriptively, and the percentage of patients with those viral mutations will be calculated.

Exploratory endpoints defined by virus titer will be summarized using descriptive statistics similar as specified for the secondary endpoints defined by SARS-CoV-2 virus RNA.

Drug susceptibility will be reported as EC₅₀ values, and respective fold-change values (ratio of EC₅₀ sample / EC₅₀ reference) will be calculated from those. A summary of drug susceptibility with summary statistics will be produced at baseline (and other timepoints, if required), together with an individual patient listing of drug susceptibility.

Exploratory Pharmacokinetic Endpoint Analyses

The exposure-response profile of AT-511 and its major metabolites will be explored (e.g., relationship between plasma concentration of AT-273 and antiviral activity) and will be reported in a standalone document separate from the CSR.

Respiratory Coinfections (Biofire)

All baseline (nasopharyngeal) samples will be tested for respiratory pathogens using the qualitative PCR-based FDA cleared BioFire FilmArray® Respiratory Panel 2 assay. This

assay detects 19 respiratory viral or bacterial pathogens. Frequency and proportions for each co-infection will be presented.

Exploratory Patient Global Impression of Severity Endpoint

The exploratory endpoint to evaluate patients' self-assessment of COVID-19 symptom severity as assessed by Patient Global Impression of Severity (PGIS) at Days 14 and 28 will be summarized using mean scores on a 4-point Likert scale: "none" (0) to "severe" (3).

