4. ANALYSIS SETS

Disposition summaries will be based on the intent-to-treat (ITT) population. All randomized patients will be included in the ITT population, and data will be summarized according to the randomized treatment assignment.

All primary and secondary virology and efficacy outcomes will be analyzed in the mITTi population. The mITTi population is defined as all patients randomized in the study who received any amount of study drug and had at least one positive SARS-CoV-2 RT-PCR test result above or equal to the limit of quantification (LOQ) during the study, with patients grouped according to the treatment assignment at randomization.

Safety analyses will be performed on the safety evaluable population, which consists of all patients who receive any amount of study drug. In all safety analyses, patients will be grouped according to the treatment that the patients actually received rather than the treatment assigned at randomization. Patients who received any dose of AT-527 will be summarized in the AT-527 group.

Pharmacokinetic analyses will be performed on the PK analysis population, which will consist of all patients in the ITT population who had at least one post-dose drug concentration measurement at a scheduled visit timepoint.

The analysis populations are defined in [Table 2](#).

Table 2 Analysis Sets

Population	Definition
ITT	All randomized patients, whether or not the patient received the assigned treatment.
Safety-evaluable	All patients who received at least one dose of study treatment.
mITTi	All patients randomized in the study that received any amount of study drug and had at least one positive central SARS-CoV-2 RT-PCR test result above or equal to the LOQ (by nasopharyngeal swab) during the study, with patients grouped according to the treatment assignment at randomization
PK population	All patients in the ITT population who had at least one post-dose drug concentration measurement at a scheduled visit timepoint

ITT=intent-to-treat; mITTi=modified intent-to-treat infected; LOQ=limit of quantification; PK=pharmacokinetic; RT-PCR=reverse-transcription polymerase chain reaction; SARS-CoV-2= severe acute respiratory syndrome coronavirus-2.

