5. STATISTICAL ANALYSES

5.1 GENERAL CONSIDERATION

All virology and efficacy analyses will be performed on the mITTi population.

All primary and secondary virology endpoints will be produced using the nasopharyngeal swab samples. Additional descriptive analyses for saliva and serum samples will be performed on an exploratory basis for the primary and secondary virology endpoints, as required. A summary of the sampling differences between cohorts is provided in [Table 3](#). Refer to Appendix 1 and Appendix 2 of the study protocol for further details.

No alpha adjustments for multiple comparisons are planned.

For all cohorts, the primary virology analysis will be performed as part of a Day 10 Review (accompanied with key safety review if deemed necessary, see [Section 5.7.1](#)) which is to be completed after all patients enrolled in the current cohort have completed assessments through Day 10. Other endpoints will be analyzed at the completion of each full cohort or at the completion of the study. All analyses at the Day 10 review or at the completion of each cohort will compare each AT-527 dose group and a combined placebo group, including all placebo patients enrolled across cohorts up to the cohort being analyzed, while analyses performed at the completion of the study will compare each AT-527 dose group and a combined placebo group from all cohorts.

Table 3 Differences in Virology Sampling Between Cohorts

Assessment	Cohort A	Cohorts B–E
Nasopharyngeal swab sample for COVID-19 virology	Once a day on Days 1, 3, 5, and 7	Once a day on Days 1, 3, 5, and 7
Saliva sample for COVID-19 virology	NA	Once a day on Days 1, 3, 5, and 7
Serum sample for anti-SARS-CoV-2 antibodies and viral RNA	Once a day on Days 1 and 7	Once a day on Days 1, 3, 5, and 7

COVID-19 = coronavirus disease 2019; NA = not applicable; SARS-CoV-2 = severe acute respiratory syndrome coronavirus-2.

For virology endpoints, the time windows for each assessment are given in [Table 4](#). The time windows will be used for all virology endpoints except the time-to-event endpoints.

Table 4 Virology Assessment Time Windows

Scheduled Timepoint ^{a, b, d}	Acceptable Time Window
Baseline (Day 1 pre-dose)	Day 1 pre-dose ^c
Day 3	Day 2 – Day 3
Day 5	Day 4 – Day 5
Day 7	Day 6 – Day 8

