5.3.2 Main Analytical Approach for Primary Virology Endpoint

The primary virology endpoint analyses will be performed on the mITTi population using the nasopharyngeal swab data.

For each cohort, the change from baseline in the amount of SARS-CoV-2 virus RNA will be compared between the AT-527 group and the pooled placebo group (meaning all placebo patients up to and including the cohort being analyzed will be used to form the placebo comparator group) at Days 3, 5, and 7 using analysis of covariance (ANCOVA) with baseline viral load as a covariate.

The least squares mean (LSM) change and its standard error (SE) of means in each group, the difference between two groups in LSM change, SE, and 80% CI, and p-values will be presented. The LSM change will be presented graphically over time.

Additionally, descriptive summaries for the change from baseline will also be presented by treatment group. The change from baseline and the amount of SARS-CoV-2 virus RNA will also be presented graphically over time.

Baseline is defined as the Day 1 (pre-dose) nasopharyngeal swab ([Table 4](#)).

If the data are not normally distributed, a non-parametric alternative method will be used (e.g., Mann-Whitney U test) to compare distributions.

The qualitative result of the SARS-CoV-2 RT-PCR test is determined using cycle threshold (Ct) values. If the qualitative result is positive, then an associated quantitative result is also provided. The quantitative result is either numerical or below the limit of quantification (BLQ). The limit of quantification (LOQ) for the virus RNA is 120 copies/ml. If the virus RNA sample has a positive qualitative result, but a quantitative result BLQ, virus RNA will be imputed as LOQ – 1 (119 copies/mL). Negative qualitative samples will be imputed as LOQ/2 (60 copies/ml) before being transformed to the log10 scale. Samples reported as positive, but not quantifiable, will contribute to qualitative summaries, but will be treated as missing (not imputed) for quantitative summaries.

Missing data will not be imputed. Any missing data will not be included in the analyses.

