5.4.2 Secondary Endpoints

5.4.2.1 Secondary Endpoints (Virology)

All secondary virology analyses will be performed on the mITTi population.

All virology analyses will be performed using the nasopharyngeal swab data.

Descriptive analyses of saliva and serum samples will be performed on an exploratory basis for the primary and secondary virology endpoints, as required.

Time to event virology secondary endpoints

For time to event virology secondary endpoints, time will be calculated in hours.

- **Time to cessation of SARS-CoV-2 viral shedding as measured by RT-PCR**
 - Time to cessation of viral shedding by RT-PCR, in hours, is defined as the time between the initiation of any study treatment and first time when a negative or BLQ test result by RT-PCR is obtained. Patients who do not receive a negative or BLQ test result by RT-PCR by the last observation timepoint will be treated as censored at the final timepoint on Day 7.
- **Time to sustained non-detectable SARS-CoV-2 virus RNA**
 - Time to sustained non-detectable SARS-CoV-2 virus RNA, in hours, is defined as the time between the initiation of any study treatment and first time when a negative or BLQ test result by RT-PCR is obtained after which no positive test above or equal to the LOQ was reported. Patients who do not meet this endpoint by the last observation timepoint will be treated as censored at the final timepoint on Day 7.

These time-to-event endpoints will be summarized using descriptive statistics by treatment, as well as Kaplan-Meier plots. The median time to response from the Kaplan-Meier plots will be presented along with the 80% CI. If required, a hazard ratio may be produced adjusting for baseline viral load using a Cox proportional hazards model.

For all cohorts, the virology time-to-event endpoints will be described for the AT-527 group and the pooled placebo group through Day 7 using the mITTi population.

For virology time to event endpoints, deaths will be right censored at Day 7. Consequently, for these endpoints, participants censored on the final day reflect two different states, death or failure to meet the improvement outcome criterion. Therefore, it is important to understand the outcome in the context of the number and timing of deaths by treatment group.

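### Time to cessation and change from baseline for virus titer, saliva and serum have no baseline-positive restriction, so patients with nothing to clear in that specimen count as early clearances and dilute the contrast

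*SAP*

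**What the plan says.** **Population.** SAP 5.1: "All virology and efficacy analyses will be performed on the mITTi population". SAP Table 2 (Section 4) admits a dosed patient who "had at least one positive central SARS-CoV-2 RT-PCR test result above or equal to the LOQ (by nasopharyngeal swab) during the study". The qualifying result may come at any visit, and the definition requires nothing about titer, saliva or serum. Protocol 6.4 uses the same population.

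**Titer.** SAP 5.5 lists change from baseline, time to cessation, proportion positive and AUC by titer, and says "Exploratory endpoints defined by virus titer will be summarized using descriptive statistics similar as specified for the secondary endpoints defined by SARS-CoV-2 virus RNA". It gives no titer limit of quantification and no value for a negative titer.

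**Saliva and serum.** SAP 5.1: "Additional descriptive analyses for saliva and serum samples will be performed on an exploratory basis for the primary and secondary virology endpoints, as required". SAP 5.4.2.1 repeats this. Table 3 shows saliva sampling in Cohorts B–E only.

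**Event rule.** Time to cessation in SAP 5.4.2.1 is "the time between the initiation of any study treatment and first time when a negative or BLQ test result by RT-PCR is obtained". No earlier positive result is required.

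**Value rule for RNA.** SAP 5.3.2: "The limit of quantification (LOQ) for the virus RNA is 120 copies/ml", and "Negative qualitative samples will be imputed as LOQ/2 (60 copies/ml) before being transformed to the log10 scale". A positive result below the LOQ is set to 119 copies/mL. Neither rule makes an exception for baseline.

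Among the exploratory virology endpoints, only drug susceptibility is limited to patients with evaluable virus.

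**The concern.** The population is defined by one specimen and assay (nasopharyngeal RNA), while the endpoints are measured by another assay (titer) or in other specimens (saliva, serum). Some patients who qualify through the swab will have no measurable titer, saliva RNA or serum RNA before the first dose. Under the event rule they achieve cessation as soon as a sample is counted. Under a constant-floor rule they contribute zero change for as long as they stay negative. Neither result says anything about the drug.

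Virus titer is a separate family of antiviral endpoints, and change in titer may be described at the Day 10 Review (SAP 5.7.1). A cessation curve that steps down by the baseline-negative share at the first sample, and a difference in change pulled toward zero, are easily misread. Neither the primary endpoint nor the sample size is affected.

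**Working it through.** **1. The plan's own sizing reproduces.** n per group = 2(z₁₋α + z_power)² × SD²/δ².
- Cohorts A–D, one-sided 10%, 80% power: δ 0.7, SD 1.2 gives 27; δ 1.1, SD 1.85 gives 26. 27/0.9 = 30.
- Cohort E (Protocol 6.1), one-sided 2.5%, δ 0.5, SD 1.25: 99, stated as 100. 100/0.9 = 111.1, rounded up to 112.

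These figures concern nasopharyngeal RNA. The documents size nothing for titer, saliva or serum.

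**2. What the rules do to one patient.** Take a patient with nasopharyngeal RNA of 2,000 copies/mL who is negative in the other assay or specimen on Days 1, 3, 5 and 7.
- Cessation: an event at the first counted sample. The SAP does not say whether the Day 1 sample can count; if not, the event falls at Day 3.
- Change, with the RNA floor: log10(60) − log10(60) = 0 at every visit.
- Variants: a below-LOQ positive at baseline followed by a negative gives log10(60) − log10(119) = −0.297. A negative baseline followed by a positive gives an increase.

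**3. Dilution of the difference in change.** Let g be the share negative at baseline in that assay or specimen. The documents do not give it; 20% to 60% is assumed. If these patients have zero change in both arms, the observed difference is (1−g) × δ.

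| g | δ = 0.7 | δ = 0.5 |
|---|---|---|
| 20% | 0.56 | 0.40 |
| 40% | 0.42 | 0.30 |
| 60% | 0.28 | 0.20 |

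**4. Dilution of cessation.** If baseline-negative patients are still negative at the first counted sample, the cumulative proportion is g + (1−g)p, where p is the proportion among baseline-positive patients. Assume p at Days 3, 5 and 7 is 0.20, 0.50, 0.70 on placebo and 0.35, 0.70, 0.85 on AT-527.
- g = 0: differences 0.15, 0.20, 0.15.
- g = 40%: 0.52, 0.70, 0.82 against 0.61, 0.82, 0.91; differences 0.09, 0.12, 0.09.
- g = 50%: already 0.60 and 0.675 at Day 3, so the median is Day 3 in both arms. At g ≥ 50% this holds for any p ≥ 0.

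**5. Illustrative power for change.** Assumed: 100 per arm, one-sided 2.5%, mean change −1.5 on placebo and −2.0 on AT-527, and SD 1.25 in baseline-positive patients. The sample size, δ, SD and alpha are borrowed from the Cohort E RNA plan.

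Unadjusted comparison: arm variance = (1−g) × 1.25² + g(1−g) × mean². At g = 40% this is 0.9375 + 0.24 × 2.25 = 1.4775 on placebo and 0.9375 + 0.24 × 4 = 1.8975 on AT-527. SE = √(3.375/100) = 0.184, and power = Φ(0.30/0.184 − 1.96) = 37%. Restricted to 60 per arm, SE = 1.25 × √(2/60) = 0.228, and power = 59%.

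ANCOVA with baseline as covariate, the method in SAP 5.3.2, was simulated with baseline titer in positives averaging 2.5 to 3.5 log10 above the floor, SD 1:

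| g | Unadjusted: full / restricted | ANCOVA: full / restricted |
|---|---|---|
| 20% | 57% / 72% | about 65% / 71% |
| 40% | 37% / 59% | about 51% / 58% |
| 60% | 23% / 43% | about 35% / 42% |

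The ANCOVA loss is about 5 to 8 points, and nearer 4 at the upper end of the assumed baseline titers. The covariate removes much of the extra variance but not the dilution: the simulated full-mITTi estimate still averages about 0.40, 0.30 and 0.20.

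**The case against.** **A titer rule is being read into silence.** The SAP 5.5 sentence borrows summary statistics from the secondary RNA endpoints. Change in RNA is the primary endpoint, and the 60 and 119 copies/mL values are RNA values. This stands in part. A reader might infer that the SAP fixes a zero titer change for these patients; it does not, because no titer floor is stated, and leaving negatives missing would give no value at all. Any constant floor does give zero, and carry-over from RNA is the natural reading. The cessation result needs no floor, only the stated event rule.

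**No test is planned.** This stands. Titer, saliva and serum summaries are descriptive, and formal tests of even the secondary endpoints are optional (SAP 5.4.1). The power figures only express loss of information. A reader might take the unadjusted loss of 15 to 22 points as the cost; the ANCOVA in SAP 5.3.2 does not support that.

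**These patients can still respond.** This stands. Enrolment is within 5 days of symptom onset, so a negative baseline can turn positive. It would be too strong to call such patients incapable of response, or to call proportion positive and AUC wrong on full mITTi. For those two endpoints, restriction is a choice of estimand.

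**The share may already be visible.** Proportion positive by visit would show it if baseline is tabulated, but that does not repair the cessation curve or the difference in change.

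**Drug susceptibility is weak precedent.** Agreed: an EC50 needs virus to measure. The point does not rest on it.

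**Conclusion.** The concern holds for time to cessation and change from baseline. For cessation it follows from the stated event rule and population once these are applied to titer, saliva or serum. For change in titer it depends on negatives taking a constant floor value, which the SAP leaves unstated. The difference in change shrinks by about (1−g), and at g of 50% or more the median time to cessation carries no treatment information. Both results assume that most baseline-negative patients stay negative. The power cost under ANCOVA is about 5 to 8 points for g of 20% to 60%; g, the effect, the SD and the baseline titers are all assumed or borrowed.

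A reader might infer that the antiviral conclusion is at risk or that one arm is favoured. The documents do not support that: these endpoints are exploratory, the primary nasopharyngeal RNA analysis is untouched, and within a cohort the expected effect is dilution.

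**What to change.** In SAP 5.5 and 5.4.2.1:
- Define time to cessation and change from baseline for titer in mITTi patients with a positive pre-dose titer. For saliva and serum, define them in mITTi patients with pre-dose RNA at or above the LOQ in that specimen.
- State the titer assay's limit and the value given to a negative titer, so that the subset and the change can be derived.
- Report the number per arm in each subset, and keep the full-mITTi summary as supportive.
- Keep proportion positive and AUC on full mITTi, show the baseline visit, and add a baseline-positive summary.

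The cost is a few sentences in the SAP and some extra tables, with no new data collection. The exploratory subsets will be smaller. Because the restriction uses a pre-dose measurement, the comparison remains randomised within a cohort, but not against placebo pooled across cohorts. The subset rule should therefore require a truly pre-dose sample: SAP Table 4 lets a sample taken up to 2 hours after dosing serve as baseline.
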